**NOTE:**

The following hospitalizations are not considered SAEs in BMS clinical studies:

- a visit to the emergency room or other hospital department < 24 hours, that does not result in admission (unless considered an important medical or life-threatening event)
- elective surgery, planned prior to signing consent
- admissions as per protocol for a planned medical/surgical procedure
- routine health assessment requiring admission for baseline/trending of health status (eg, routine colonoscopy)
- medical/surgical admission other than to remedy ill health and planned prior to entry into the study. Appropriate documentation is required in these cases
- admission encountered for another life circumstance that carries no bearing on health status and requires no medical/surgical intervention (eg, lack of housing, economic inadequacy, caregiver respite, family circumstances, administrative reason).

### **6.1.1 Serious Adverse Event Collection and Reporting**

Sections 5.6.1 and 5.6.2 in the Investigator Brochure (IB) represent the Reference Safety Information to determine expectedness of serious adverse events for expedited reporting. Following the subject's written consent to participate in the study, all SAEs, whether related or not related to study drug, must be collected, including those thought to be associated with protocol-specified procedures. All SAEs must be collected that occur during the screening period and within 90 days of discontinuation of dosing. If applicable, SAEs must be collected that relate to any later protocol-specified procedure (eg, a follow-up skin biopsy).

The investigator should report any SAE that occurs after these time periods and that is believed to be related to study drug or protocol-specified procedure on the BMS GPVE form RD-FRM-SOP-006991-5.

The paper form (GPVE form RD-FRM-SOP-006991-5) should be submitted immediately, within 24 hours. The original paper forms are to remain on site. Pregnancies are to be reported on a Pregnancy Surveillance Form RD-FRM-SOP-006991-4 [007177] paper form).

The paper forms are to be transmitted via email or confirmed facsimile (fax) transmission to:

**SAE Email Address:** [contact]

**SAE Facsimile Transmission, Central Facsimile Station:** [contact]

SAE Global 24 hour telephone number: International: [contact]

**SAE Telephone Contact** (required for SAE and pregnancy reporting): Refer to Contact Information list.

If only limited information is initially available, follow-up reports are required. (Note: Follow-up SAE reports should include the same investigator term(s) initially reported.)

If an ongoing SAE changes in its intensity or relationship to study drug or if new information becomes available, a follow-up SAE report should be sent within 24 hours to the BMS (or designee) using the same procedure used for transmitting the initial SAE report.

All SAEs should be followed to resolution or stabilization.

## **6.2 Nonserious Adverse Events**

A *nonserious adverse event* is an AE not classified as serious.

### **6.2.1 Nonserious Adverse Event Collection and Reporting**

Nonserious AEs should be followed to resolution or stabilization, or reported as SAEs if they become serious (see [Section 6.1.1](#)). Follow-up is also required for nonserious AEs that cause interruption or discontinuation of study drug and for those present at the end of study treatment as appropriate. All nonserious AEs that are not listed in the IB as expected must be recorded and described on the nonserious AE page of the GPVE form RD-FRM-SOP-006991-5.

## **6.3 Laboratory Test Result Abnormalities**

The following laboratory test result abnormalities should be captured on the GPVE form RD-FRM-SOP-006991-5, as appropriate:

- Any laboratory test result that is clinically significant or meets the definition of an SAE
- Any laboratory test result abnormality that required the subject to have drug discontinued or interrupted
- Any laboratory test result abnormality that required the subject to receive specific corrective therapy.

It is expected that wherever possible, the clinical rather than laboratory term would be used by the reporting investigator (eg, anemia versus low hemoglobin value).

These procedures are considered standard of care and are recommended, but are not mandatory.

#### **6.4 Pregnancy**

If, following initiation of the study drug, it is subsequently discovered that a study subject is pregnant or may have been pregnant at the time of study exposure, including during at least 5 half lives after product administration, the investigator must immediately notify the BMS Medical Monitor/designee of this event and complete and forward a Pregnancy Surveillance Form to BMS Designee within 24 hours of awareness of the event and in accordance with SAE reporting procedures described in [Section 6.1.1](#).

In most cases, the study drug will be permanently discontinued in an appropriate manner (eg, dose tapering if necessary for subject safety).

In the rare event that the benefit of continuing study drug is thought to outweigh the risk, after consultation with BMS, the pregnant subject may continue study drug after a thorough discussion of benefits and risk with the subject.

Protocol-required procedures for study discontinuation and follow-up must be performed on the subject unless contraindicated by pregnancy (eg, x-ray studies). Other appropriate pregnancy follow-up procedures should be considered if indicated.

The investigator must immediately notify the BMS Medical Monitor (or designee) of this event and complete and forward a Pregnancy Surveillance Form (RD-FRM-SOP-006991-4 [007177] paper form) to BMS (or designee) within 24 hours and in accordance with SAE reporting procedures described in [Section 6.1.1](#).

Follow-up information regarding the course of the pregnancy, including perinatal and neonatal outcome and, where applicable, offspring information must be reported on the Pregnancy Surveillance Form.

Any pregnancy that occurs in a female partner of a male study participant should be reported to BMS. Information on this pregnancy will be collected on the Pregnancy Surveillance Form.

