#### 1. Target Population

- Initial objective response (PR or CR, confirmation not required) or stable disease of  $\geq 3$  months (beginning Week 12 with SD at Week 24) is achieved after the Induction phase *and*
- Subsequent documented progression (per RECIST v1.1)
  - Progressive Disease (PD): Requires that there is  $\geq 20\%$  increase in the sum of longest diameter of all target lesions AND an absolute increase of at least 5 mm of tumor size, taking as reference the smallest sum of the longest diameter recorded at or following baseline or the appearance of one or more new lesions.
  - For subjects that have non-measurable disease only at baseline, progression will be determined per (Section 5.4). These subjects are not eligible for Re-Induction if they progress earlier than Week 24.
  - Progressive disease does not require confirmatory scans, however, if the investigator determines that PD is questionable (eg, pseudoprogression), then they may opt to do confirmatory scans no less than 4 weeks since the prior scan in order to verify the reliability of the radiologic finding. Once PD is confirmed, the patient should be re-induced within 28 days and meet all Re-induction eligibility criteria.
- Did not experience any adverse events as described in Section 4.3.2.3 (Permanent Discontinuation of Ipilimumab) or experience a dose delay  $> 21$  days due to toxicity as described in Section 4.3.2.1 (Withholding Dosing of Ipilimumab)
- Did not discontinue ipilimumab for any reason

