### **3.5 Discontinuation of Subjects from Treatment**

Subjects MUST discontinue investigational product (and non-investigational product at the discretion of the investigator) for any of the following reasons:

- Subject's request to stop study treatment
- Any clinical AE, laboratory abnormality or intercurrent illness which, in the opinion of the investigator, indicates that continued participation in the study is not in the best interest of the subject
- Pregnancy
- Termination of the study by BMS
- Loss of ability to freely provide consent through imprisonment or involuntarily incarceration for treatment of either a psychiatric or physical (eg, infectious disease) illness
- Progressive Disease by RECIST v1.1.
- Unacceptable toxicity, as defined in protocol [Section 4.3](#) for ipilimumab, and as defined in the product label for the chosen chemotherapy.

All subjects who discontinue investigational product should comply with protocol specified follow-up procedures as outlined in [Section 5](#). The only exception to this requirement is when a subject withdraws consent for all study procedures including post-treatment study follow-up or loses the ability to consent freely (ie, is imprisoned or involuntarily incarcerated for the treatment of either a psychiatric or physical illness).

If study treatment is discontinued prior to the subject's completion of the study, the reason for the discontinuation must be documented in the subject's medical records.

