### **4.3 Selection and Timing of Dose for Each Subject**

#### **4.3.1 Ipilimumab**

Ipilimumab will be supplied by BMS.

Subjects randomized to the ipilimumab arm will receive ipilimumab at a dose of 3 mg/kg via a 90-minute infusion every 3 weeks x 4 (Week 1, Week 4, Week 7, and Week 10) unless there is confirmed disease progression (per RECIST v1.1), unacceptable toxicity or any of the other criteria as specified in [Section 3.5](#) are met.

Ipilimumab is to be administered as a 90-minute IV infusion, using a volumetric pump with a 0.2 to 1.2 micron in-line filter at the protocol-specified dose. Alternatively a gravity infusion pump is also allowed provided that the site ensures that the whole planned dose is administered. The drug can be diluted with 0.9% normal saline or 5% Dextrose Injection to concentrations between 1 mg/mL and 4 mg/mL. It is not to be administered as an IV push or bolus injection. Care must be taken to assure sterility of the prepared solutions, since the drug product does not

contain any antimicrobial preservatives or bacteriostatic agents. At the end of the infusion, flush the line with a sufficient quantity of normal saline or 5% dextrose solution;

Ipilimumab injection can be used for IV administration without dilution after transferring to a PVC (polyvinyl chloride), non-PVC/non-DEHP (di-(2-ethylhexyl)phthalate) or glass containers and is stable for 24 hours at 2° - 8°C or room temperature/room light (RT/RL). For ipilimumab storage instructions, refer to ipilimumab IB and/or pharmacy reference sheets.

Recommended safety measures for preparation and handling include protective clothing, gloves, and safety cabinets.

Infusion volume may be calculated by: total dose in mg divided by 5 mg/mL = infusion volume.

- If the subject weight on the day of dosing differs by > 10% from the weight used to calculate the dose, the dose must be recalculated.

Refer to the Investigator Brochure and Drug Preparation Guidelines for detailed information.

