#### **4.3.2 Dose Modification Criteria - Ipilimumab**

##### **4.3.2.1 Withholding Dosing of Ipilimumab**

At the discretion of the investigator, it *may be necessary* to withhold (maximum 21 days) ipilimumab dosing for the following adverse event(s) considered related to ipilimumab:

- Any Grade 2 non-skin adverse event except for laboratory abnormalities;
- Grade 2 AST, ALT, or Total bilirubin elevation in laboratory values (unless present at baseline);
- Any ≥ Grade 3 laboratory abnormality.

*It is necessary* to withhold (maximum 21 days) ipilimumab dosing for the following adverse events:

- Any ≥ Grade 3 skin adverse event regardless of causality;
- Any adverse event, laboratory abnormality or intercurrent illness which, in the judgment of the investigator, warrants withholding the dose of study medication.

If treatment must be delay for > 21 days (> 42 days from previous dose), please contact the medical monitor before resuming dosing.

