#### **4.3.2.3 Permanent Discontinuation of Ipilimumab**

Ipilimumab must be permanently discontinued for any of the following:

1. Adverse event(s) considered related to ipilimumab as described below:
  - Any  $\geq$  Grade 2 eye pain or reduction of visual acuity that does not respond to topical therapy and does not improve to Grade 1 severity within 2 weeks of starting therapy OR requires systemic treatment;
  - Any  $\geq$  Grade 3 bronchospasm or other hypersensitivity reaction;
  - Any other  $\geq$  Grade 3 non-skin adverse event with the exception of laboratory abnormalities and symptomatic endocrinopathies which resolve (with or without hormone substitution); subjects with an adrenal crisis where symptoms resolve (with or without hormone substitution) may resume ipilimumab treatment as well;
  - Any Grade 4 laboratory abnormalities, except AST, ALT, or total bilirubin;
    - AST or ALT  $>$  8 x ULN,
    - Total bilirubin  $>$  5 x ULN;
  - Any other Grade 4 adverse event;
  - Subject experiences an allergic/infusion reaction while receiving study drug at a slower infusion rate due to a prior allergic/infusion reaction;
2. Adverse event(s) regardless of relationship to ipilimumab as described below:
  - Any motor neurologic toxicity  $\geq$  Grade 3 regardless of causality;
  - Any adverse event, laboratory abnormality or intercurrent illness which, in the judgment of the investigator, presents a substantial clinical risk to the subject with continued study drug dosing;
  - Any  $\geq$  Grade 3 treatment related sensory neurologic toxicity;
3. Drug related toxicity that prevents administration of ipilimumab for  $>$  21 days from the scheduled dose.
4. Confirmed and documented progression of disease on ipilimumab retreatment, per RECIST v1.1 criteria.

Experience is limited for continuing ipilimumab in subjects who have experienced Grade 3 - 4 endocrine toxicities (eg, adrenal crisis). In these situations, the medical monitor should be consulted before continuing treatment with ipilimumab.

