**Table 5.1-1: Procedural Outline - Re-Induction Phase (CA184248)**

Procedure	Re-Induction Phase ( ipilimumab arm only ) (± 3 days)					End of Treatment Visit	Toxicity/ Progression Follow-up (± 14 days)	Notes
	D1/ W1	D22/ W4	D43/ W7	D64/ W10	D78/ W12			
Laboratory Tests								
Hematology, Chemistry	X	X	X	X		X		Results of safety laboratory collections (ie, Chemistry and Hematology) must be obtained and reviewed prior to dosing.
Endocrine	X	X	X	X				Section 5.3.7.3
HIV, hepatitis C antibody, hepatitis B surface antigen (HBsAg)								To be repeated during the course of the study if clinically indicated.
Pregnancy Test	X	X	X	X		X		Section 3.3 Women of childbearing potential must have a negative pregnancy test within 24 hours prior to study drug dosing.
Efficacy Assessments								
Section 5.4.2.1. Tumor assessments will be based on RECIST v1.1 criteria. Confirmatory scans are not required. TAs will be performed every 12 weeks or per standard of care until documented PD or withdrawal of consent.								
Clinical Drug Supplies								
Ipilimumab	X	X	X	X				Subjects are eligible to receive only one course of Re-Induction therapy only

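### Protocol Section 6.4 lets a pregnant subject continue ipilimumab, although Section 3.5 makes pregnancy a mandatory reason to stop and Table 5.1-1 requires a negative test before dosing

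*Protocol*

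**What the plan says.** Section 6.4 of the protocol covers a subject found, after study drug has been started, to be pregnant or possibly pregnant at the time of exposure. Its default is qualified: "In most cases, the study drug will be permanently discontinued in an appropriate manner (eg, dose tapering if necessary for subject safety"). The next sentence gives an exception for a rare case in which benefit is thought to outweigh risk: "after consultation with BMS, the pregnant subject may continue study drug after a thorough discussion of benefits and risk with the subject".

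Section 3.5 is absolute: "Subjects MUST discontinue investigational product (and non-investigational product at the discretion of the investigator) for any of the following reasons". Pregnancy is one of the listed reasons and carries no qualifier.

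Section 4.3.1 gives ipilimumab every three weeks for four doses "unless there is confirmed disease progression (per RECIST v1.1), unacceptable toxicity or any of the other criteria as specified in" Section 3.5.

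The pregnancy-test row of Table 5.1-1 adds: "Women of childbearing potential must have a negative pregnancy test within 24 hours prior to study drug dosing". Section 5.3.5 covers the same tests in the body of the protocol. It requires a negative result within 24 hours before the start of study drug, and a test within 24 hours before dosing at every administration visit.

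Section 4.1.1 names ipilimumab as the investigational product in this version. Sections 3.5 and 6.4 do not refer to each other.

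**The concern.** A site that learns during Re-Induction that a subject is pregnant finds two instructions. Section 3.5 tells it to stop. Section 6.4 tells it that stopping is usual and that dosing may go on if the sponsor and the subject agree. A site and medical monitor acting in good faith on Section 6.4 could give a dose that Section 3.5 forbids and that does not meet the test requirement in Table 5.1-1.

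What is at stake is possible fetal exposure to ipilimumab, and a protocol deviation created by following the protocol. Section 9.1.1 tells the investigator not to deviate without prior ethics approval, except to remove an immediate hazard. A site using the Section 6.4 exception would have no clear answer on whether it had deviated.

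**Working it through.** There is no statistical figure to reproduce. The check is a comparison of clauses, followed by a count of the doses at issue.

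**Clauses side by side, for a subject with a confirmed pregnancy during Re-Induction**

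| Place | Instruction | May she receive the next dose? |
|---|---|---|
| 3.5 | Mandatory discontinuation; pregnancy listed without exception | No |
| 4.3.1 | Dosing subject to the 3.5 criteria | No, but only because of 3.5 |
| Table 5.1-1, note | Negative test within 24 hours before dosing | No |
| 5.3.5 | Negative test before the start of drug; a test before each dose | Test required; for later doses the result needed is not restated |
| 6.4 | Usually stop; may continue after sponsor consultation and discussion with the subject | Yes, in a rare case |

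1. *Same drug.* Ipilimumab is the only investigational product in this version, so the clauses cannot be separated by product.
2. *Same person.* The definition in Section 3.3.3 turns on menarche, surgical sterilization and menopause. A pregnant woman still meets it, so the Table 5.1-1 note applies to her.
3. *Independent prohibitions.* There are two: Section 3.5 and the Table 5.1-1 note. Section 4.3.1 repeats Section 3.5 by cross-reference and is not a third.
4. *Eligibility does not settle it.* Section 3.3.2 refers Re-Induction exclusions to Section 3.3.2.1, which does not list pregnancy. In this phase the protection rests mainly on Section 3.5 and the tests before dosing.
5. *Which course breaches nothing.* Section 6.4 only permits continuation. A site that always stops complies with every clause. A site that uses the exception breaks Section 3.5 and the table note.

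**Doses at issue**

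- Subjects eligible for Re-Induction (Section 8.1): 2.
- Doses per subject (Section 3.1): up to 4, in one course only.
- Dose 1 is excluded. Section 5.3.5 requires a negative test before drug is started, and Section 6.4 speaks of continuing drug. That leaves doses 2 to 4, so 4 − 1 = 3 doses per subject.
- Upper limit: 2 × 3 = 6 doses.
- Lower limit: 0. Re-Induction begins only on documented progression, and the documents do not say whether either subject has progressed or is a woman of childbearing potential.

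**Effect on analyses**

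The database was locked on 03Jun2019 (Sections 1.2 and 5.4.1), before this version was issued on 28-Jun-2019. Sections 8.2 and 8.4.2 plan no analysis of Re-Induction. The effect on any endpoint, on power or on the type I error is nil.

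**The case against.** The strongest reply is that Section 6.4, as the specific clause, qualifies the general list in Section 3.5, and that its exception is guarded by sponsor consultation and a discussion with the subject. The safeguards are real and make misuse unlikely. They do not remove the conflict: no rule of precedence is stated, and the Table 5.1-1 note has no exception, so it would still bar the dose.

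A second reply is that Section 5.3.5 asks for a negative result only before the start of drug. That is correct and weakens the support from testing, which rests on the table note alone for doses 2 to 4. Section 3.5 is unaffected.

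A third reply is that either section could be changed. This stands in part. The mention of tapering in Section 6.4 suggests generic wording, since Section 4.3.2 offers only withholding, resuming or permanent discontinuation. But Section 3.5 also carries a leftover reference to a chemotherapy label, so generic origin does not show which clause was intended. The reasons for changing Section 6.4 are that stopping already satisfies every clause, and that keeping the exception would mean writing it into at least Section 3.5 and Table 5.1-1.

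A reader might infer two stronger points that the documents do not support.

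- *That up to 8 doses (2 × 4) are at issue,* by counting Induction dosing as initiation of study drug. A subject in follow-up after Induction is not on drug, so the first Re-Induction dose would start a new course and not continue one. It also needs a prior negative test.
- *That the rule on long delays is a similar contradiction.* Section 4.3.2.1 ends "If treatment must be delay for > 21 days (> 42 days from previous dose), please contact the medical monitor before resuming dosing" and names no cause, while Section 4.3.2.3 item 3 stops treatment for "Drug related toxicity that prevents administration of ipilimumab for" more than 21 days. The thresholds coincide (21-day interval + 21-day delay = 42 days). But Section 4.3.2.3 is mandatory and specific to drug-related toxicity, and Section 4.3.2.1 itself caps withholding at 21 days. The contact step still has a use for delays with other causes.

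**Conclusion.** The contradiction holds as a matter of text in the current protocol, with high confidence: Section 6.4 permits dosing that Section 3.5 and the Table 5.1-1 note rule out. Confidence is lower on which clause the sponsor meant to govern. Changing Section 6.4 is recommended as the safer and smaller correction, not because the documents prove that intent.

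The size is 0 to 6 doses. The upper limit assumes that both subjects are women of childbearing potential, both enter Re-Induction and become pregnant after dose 1, and the exception is used for every remaining dose. The realistic number may well be zero. The point merits correction because it concerns subject safety and is cheap to fix. It has no bearing on the trial's results.

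**What to change.** In Section 6.4:

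1. Replace the sentence that sets the qualified default with: *If pregnancy is confirmed, ipilimumab must be permanently discontinued (see Section 3.5).*
2. Delete the next sentence, which allows a pregnant subject to continue.
3. Leave the rest unchanged: immediate notification, the surveillance form, discontinuation procedures and pregnancy follow-up, including for a subject who may have been pregnant at exposure.

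The condition that pregnancy is confirmed matters. The opening of Section 6.4 also covers a possible past pregnancy, and an unconditional order to stop and not restart would reach further than Section 3.5 does. Permanence is already the section's own default.

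Sections 3.5, 4.3.1 and 4.3.2, Table 5.1-1 and the SAP need no change. The cost is one sentence replaced and one deleted in a site-specific protocol, with IRB/IEC review under Section 9.1.1. No new data or re-analysis is needed, and the change could be made with any other amendment.
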